- to evaluate the safety of the proposed regimen of preventive therapy with Ingaron (INN: human recombinant interferon gamma, lyophilizate for the preparation of solution for intranasal administration of 100,000 IU) in adult volunteers. Safety is assessed based on adverse events, clinically significant changes in laboratory parameters during the study, taking into account the assessment of severity according to the STCAE 4.03 scale.

OBJECTIVES OF NON-INTERVENTIONAL RESEARCH

Primary objective

To evaluate the effectiveness of the prophylactic use of Ingaron (INN: human recombinant interferon gamma, lyophilizate for the preparation of solution for intranasal administration of 100,000 IU) in the mode of 3 drops in each nasal passage intranasally every other day for 10 days with break of 7 days (2 10-day cycles) in adult volunteers.

Secondary objectives

Safety assessment of the prophylactic use of Ingaron (INN: human recombinant interferon gamma; lyophilizate for the preparation of a solution for intranasal administration of 100,000 IU), applied 3 drops into each nasal passage intranasally every other day for 10 days with break of 7 days (two 10-day cycles) in adult volunteers.

Efficacy and safety include evaluation based on epidemiological, anamnestic, and clinical data, as well as laboratory studies and specialized scales.

DESIGN OF A NON-INTERVENTIONAL STUDY

Post-marketing prospective randomized open-label comparative non-interventional study in parallel groups.

A total of 4 visits are planned (0–3). Visit 0 and 1 can be combined.

Main stages of the study

1. Visit 0. Conducted in person⁷. Screening: informed consent, inclusion of volunteers and distribution into groups (Day -3-1)
2. Visit 1. Conducted in person. Randomization. Delivery of the investigated drug and the diary of the researcher participant (Day 0)
3. Visit 2. It is carried out remotely (by phone). Completion of a preventive course, evaluation of preventive efficacy and safety during the period of drug administration. The beginning of the observation period. (Day 28–30)
4. Visit 3. Conducted in person. Completion of the observation and research period. (Day 56–62)

The main procedures and stages of the study are reflected in the Schedule of research procedures.

The total duration of participation is about 2 months (56–62 days).

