For participants who have a case of ARVI (COVID-19), visit 3 can be carried out earlier or later, but the total duration of the study should not be more than 90 days. Up to this point, medical researcher should try to collect the most complete information about the patient's condition. If it is not possible to conduct a face-to-face visit, final visit is conducted remotely.

Schedule of research procedures

| Visit number | 0 | 1 | 2 | 3 |
|---|-----------|---------------|--|--|
| Setting | In person | In person | Phone call | In person |
| Visit name | Screening | Randomization | The end of the course of prevention Beginning of the observation period | End of the observation period Completion of the study |
| Study days | -3-1(0) | 0 | 27 (+/-3) | 56-62* |
| Informed consent ¹ | + | | | |
| Anamnesis ² | + | | | |
| Complaints | + | + | + | + |
| Physical examination ³ | + | + | | + |
| Pregnancy test | + | | | |
| Safety assessment | + | + | + | + |
| Analysis for RNA to SARS-CoV-2 ⁴ | + | | | + |
| Checking the inclusion/non-inclusion criteria | + | + | | |
| Checking exclusion criteria | | | + | |

⁷ A full-time visit can be carried out both at the research center and at home

| | | | | |
|--|---|---|---|----------------|
| Randomization | | + | | |
| Delivery of the study drug ⁵ | | + | | + |
| Compliance assessment | | | + | + |
| Issue of the participant's diary | | + | | |
| Effectiveness evaluation | | | + | + |
| Assessment of the participant's condition according to the WHO scale | + | + | + | + ⁷ |
| Return of study drug and diary | | | | + |

* For patients with a registered case of ARVI, duration of participation in the study may be longer, but not exceed 90 days

- 1 All research procedures, except routine laboratory and instrumental studies, the data of which are used to assess the condition of the study participant, are performed after the procedure of signing the informed consent of the patient
- 2 The study should indicate the epidemiological history of respiratory viral diseases, status of vaccination (influenza, pneumonia, COVID-19), use of means of nonspecific protection and prevention of acute respiratory viral infections, including COVID-19

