Randomization of the study participants is carried out on the same day or the next day after signing the informed consent, but no later than 3 days from the date of material sampling to the PCR test.

Randomization is carried out according to the Randomization List version 1.00 from 16.11.2020. To randomize a participant into a study, a research physician must contact the employee responsible for randomization (instructions for randomization are provided by the sponsor to the center before the start of the study) by phone and provide the study code and the researcher's full name for identification, as well as the data of the randomized participant: screening number, initials, date of birth. The researcher is informed of the assigned randomization number of the participant and the number of the prevention group (I or II). After the call, a Randomization Form is sent to the researcher's email as confirmation. The form must be printed out, signed by the researcher, and attached to the primary documentation of the participant.

The intake of the study drug is carried out independently by the participant at home, with the Diary of the participant of the study.

Other preventive measures

Any non-specific measures for the prevention of a new coronavirus infection COVID-19 are allowed, including personal protective equipment (respirators, glasses, gloves, protective suits).

Previous therapy

As a previous therapy, it is prohibited to take any drug with test status 1 month before participating in this study.

Concomitant therapy

According to the design of the non-interventional study, participants can receive any concomitant therapy for concomitant chronic diseases, except medications prescribed off-label or for research purposes.

Prohibited therapy

For the study group: use of any medications that may or may have preventive effects against ARVI, including COVID-19, is **prohibited**; use of non-specific methods of preventive protection is **not prohibited**.

For the control group: use of interferon gamma is **prohibited**; use of any medications that may or may have preventive effects against ARVI, including COVID-19, as well as the use of non-specific methods of preventive protection is **not prohibited**.

All preventive measures, including pharmacotherapeutic ones, should be indicated in the diary filled in by the participant.

Exclusion criteria

A participant should be excluded from the study if at least one of the following criteria is met:

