In case of a positive PCR test before the start of the drug, volunteer is not included in the study, is isolated and falls under the supervision of a district doctor. In case of a positive PCR test during or after the preventive course, volunteer continues to participate in the study, is isolated under observation and, if possible, comes to visit 3 after the quarantine is lifted (at least 14 days from the date of signing Consent for the treatment of a new coronavirus infection COVID-19 in outpatient conditions (at home) and observing the isolation regime or discharge from the hospital in case of laboratory confirmation of COVID-19) with the provision of data on their condition to the researcher coordinator.

STUDY POPULATION

Adult volunteers who do not have clinical symptoms of ARVI.

Inclusion criteria

1. Volunteers of both genders over 18 years old.
2. Obtaining a written form of informed consent.
3. Ability and consent to participate in this study.
4. No symptoms of respiratory infection.
5. A negative result of a PCR study for the presence of SARS-CoV-2 RNA according to the biomaterial obtained by nasopharyngeal ⁹smear.

Non-inclusion criteria

1. Any other concomitant diseases or conditions that, in the opinion of the research doctor, may distort the results of the study, restrict the rights of the volunteer, or put him at greater risk.
2. Contraindications to the use of the study drug.
3. Individual intolerance of the ingredients included in the composition of the study drug.
4. Pregnancy or breast-feeding.
5. Controversial result of PCR test for the presence of SARS-CoV-2 RNA according to the biomaterial obtained by nasopharyngeal smear.
6. Participation in a clinical trial using the investigated therapy for 30 days prior to inclusion in this study.
7. Disagreement on following reliable contraceptive measures in the framework of the study

⁹ It is permissible to accept the results of a nasal or pharyngeal smear, as well as the results of studies performed before inclusion in the study for no more than 72 hours.

(sexual abstinence; or a combination of 2 different methods: for example, barrier and spermicides, or barrier and intrauterine device, or barrier and hormonal, etc.) – for participants with preserved childbearing potential.

Number of participants

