1. The proportion of patients with confirmed COVID-19 at the end of the period of preventive treatment of the drug (measurement period: 28 days).
2. The proportion of patients with acute respiratory viral infections, including COVID-19, at the end of the follow-up period (change period: 2 months).
3. The proportion of patients with confirmed COVID-19 at the end of the follow-up period (change period: 2 months).
4. Frequency of development of complicated course of ARVI.
5. The proportion of participants with each of the scores (0-8) according to the WHO Clinical Improvement Scale (change period: 28 days).
6. The proportion of participants with each of the scores (0-8) according to the WHO Clinical Improvement Scale (change period: 2 months).
7. Duration of symptoms of the disease of study participants who had acute respiratory viral infections, including COVID-19 (change period: 2 months).
8. The duration of the symptoms of the disease of the study participants who were infected with ARVI, including COVID-19 (measurement period: 28 days).

Confirmation of clinical cases of ARVI, including COVID-19:

In the following cases:

- 1) a positive result of PCR on SARS-CoV-2 RNA, regardless of the presence of clinical symptoms;
- 2) appearance of clinical symptoms of ARVI in the absence of a PCR result on SARS-CoV-2 RNA or in the case of a negative result on SARS-CoV-2 RNA, -

at any stage during participation in the study, a completion visit (Visit 3) is conducted at the end of the quarantine period (at least 14 days from the date of signing Consent for the treatment of a new COVID-19 coronavirus infection in outpatient settings (at home) and compliance with the isolation regime or discharge from the hospital in case of laboratory confirmation of COVID-19), at which the patient returns the participant's diary and reports his condition to the doctor-researcher, transmits information about hospitalization, duration of symptoms, results of tests and performed studies.

Definition of the COVID-19 case:

Suspicious case of COVID-19

Body temperature above 37.5° in addition to one or more of the following signs (in the absence of other known causes that explain the clinical picture, regardless of the epidemiological history):

- Cough (dry or with scant sputum)
- Shortness of breath
- Feeling of congestion in the chest
- SpO₂ no more than 95%
- Sore throat
- Nasal stuffiness or moderate rhinorrhea
- Smell disorders or anosmia
- Ageusia
- Conjunctivitis
- Fatigue

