4. Open the vial of water for injection by breaking off its upper part.
5. Pour 5 ml of water for injection into glass vial with a dry substance.
6. Remove the dropper cap from the package and fix it on the neck of the bottle.

Due to the need to store the active substance in a full vacuum, the aluminum cap must be hermetic and durable. Slowly remove the aluminum guard of the bottle, avoid cuts. If the cap breaks off during removal, you can remove the rest of the metal cap with scissors.

Take vial with Ingaron with liquid inside with both hands and turn it over 10–15 times.

Put the vial with Ingaron with the liquid inside in the refrigerator and store there for 10 days. For the second course of prevention (after 1 week), use the second vial.

Return the empty ampoules of water for injection together with the used glass vials to the researcher at the next visit.

Administration

Course 1. The drug is applied 3 drops in each nasal passage every other day 30 minutes before breakfast for 10 days (total of 5 instillations). The use of the drug is carried out according to the following regimen:

- Course 1. Day 1 – mark administration time in your diary
- Course 1. Day 3 – mark administration time in your diary
- Course 1. Day 5 – mark administration time in your diary
- Course 1. Day 7 – mark administration time in your diary
- Course 1. Day 9 – mark administration time in your diary

This is 1 preventive cycle. Then a break of 7 days.

Course 2. Drug administration is carried out similarly to Course 1. Preparation of the drug is carried out similarly to the algorithm described earlier. Dosage regimen is the same:

- Course 2. Day 1 – mark administration time in your diary
- Course 2. Day 3 – mark administration time in your diary
- Course 2. Day 5 – mark administration time in your diary
- Course 2. Day 7 – mark administration time in your diary
- Course 2. Day 9 – mark administration time in your diary

If you missed drug administration, mark the day in your diary with a "check mark" and take the next dose the next morning 30 minutes before breakfast and then continue using it every other day. Remember that the finished solution of the drug is stored for no more than 10 days in the refrigerator. Do not use it after the expiration date. For Course 2, use the second bottle, do not use the first bottle, even if the drug is not fully used.

| | |
|---------------------------------|---|
| Course 1 Day 1 | Date ____ ____ ____ ____ ____ ____ day month year |

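### The positive-PCR rule and the SAP's ITT definition are tied to drug use, not randomisation, so an early Group I case could be dropped where the same Group II case counts

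*Protocol*

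**What the plan says.** The Protocol, section Nasopharyngeal smear, closes with two rules for a positive PCR. The first is "In case of a positive PCR test before the start of the drug, volunteer is not included in the study, is isolated". The second is "In case of a positive PCR test during or after the preventive course, volunteer continues to participate in the study". Neither mentions randomisation.

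The following places bear on how these rules act:

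- **Drug start.** Under Randomization of study participants, Group I uses the drug and Group II does not. The drug is handed out at Visit 1, the randomisation visit, and taken independently at home. Appendix 1 sets dosing 30 minutes before breakfast. No date is fixed for the first dose.
- **Case counting.** The section Confirmation of clinical cases of ARVI, including COVID-19 (repeated in SAP section 3.2) lists "a positive result of PCR on SARS-CoV-2 RNA, regardless of the presence of clinical symptoms", at any stage of participation and without restriction by group. The later paragraph on antibody testing explains the time during or after the preventive course as running from randomisation to the end of observation.
- **Analysis sets.** The Protocol's main efficacy set (FAS) is everyone included in the study. SAP section 5.5 makes ITT the main set and limits it to randomised participants who had exposure to the study drug.
- **Testing.** In the Schedule of research procedures, the row "Analysis for RNA to SARS-CoV-2" is marked at Visits 0 and 3 only.

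**The concern.** In a randomised comparison, follow-up for the endpoint should begin at the same moment in both groups, and that moment is randomisation. Here one rule decides whether a positive PCR means non-inclusion or continued participation, and it is tied to an event that only one group has. The interval between randomisation and first dose exists in Group I and has no counterpart in Group II.

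The two texts can act together. A Group I volunteer who is positive in that interval is, on the literal wording, not included. If the volunteer is then not started on the drug, he or she is unexposed and falls outside the SAP's ITT set. In Group II the exposure condition cannot be applied at all, since it would empty the group, so it has to be ignored there. A condition enforced in one group and ignored in the other can remove events from one side only. The loss would touch the primary endpoint and confirmed COVID-19, and its direction would favour the drug.

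**Working it through.** **1. Which rule governs a positive PCR after randomisation and before a first dose?**

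| Text | Time anchor | Group I | Group II |
|---|---|---|---|
| Protocol, Nasopharyngeal smear, first rule | Start of drug | Not included (literal reading) | No drug start, so no defined cut-off |
| SAP 5.5, ITT | Exposure to drug | Outside ITT if never dosed | Condition cannot apply |
| Protocol, Confirmation of clinical cases; SAP 3.2 | Participation | Case | Case |
| Antibody-testing paragraph, same sections | After randomisation | Within the registration period | Within the registration period |

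The first two rows conflict with the last two. The notes to SAP Tables 20 and 21 show the same unequal anchors for adverse events: after at least one use of the drug in the study group, and from randomisation in the control group.

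**2. Number per group.** The Protocol's printed formula with 5% against 2% and t = 1.96 gives (0.05 × 0.95 + 0.02 × 0.98) × 1.96² / 0.03² = 0.0671 × 3.8416 / 0.0009 = 286.4. Then 286 × 1.1 = 314.6, or 315 randomised per group. The plan's 286 and 315 are reproduced. Only the 315 is used below.

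**3. Length of the gap.** The documents do not give it. Dosing before breakfast after a daytime Visit 1 suggests at least one day. An indirect limit comes from the schedule: a 27-day course starting on Day s ends on Day s + 26, and Visit 2, which closes the course, falls no later than Day 30, so s is at most 4. No text enforces this. Gaps of 1 and 3 days are therefore assumptions.

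**4. Cases falling in the gap.** Assume a constant hazard over 28 days and 315 participants in Group I. With incidence p and gap d, the fraction falling ill in the gap is e = 1 − (1 − p)^(d/28), and the cases at risk of removal are 315 × e. The range 1 to 5% is the control incidence in the Protocol's section Number of participants.

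| 28-day incidence | Expected cases in 315 | 1-day gap | 3-day gap |
|---|---|---|---|
| 1% | 3.15 | 0.11 | 0.34 |
| 5% | 15.75 | 0.58 | 1.73 |

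For this population and hazard these are upper figures, because they treat every ARVI case in the gap as PCR-positive and as detected before the first dose.

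**5. Effect on the comparison if all of these were removed.** Suppose the true rate is 5% in both groups. Taking the gap cases out of numerator and denominator gives a Group I rate of (p − e)/(1 − e).

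- 1 day: (0.05 − 0.00183)/0.99817 = 4.83%, a risk ratio of 0.965.
- 3 days: (0.05 − 0.00548)/0.99452 = 4.48%, a risk ratio of 0.895.

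Exact enumeration of the binomial outcomes, using the uncorrected chi-squared test at two-sided 5%, gives the chance of a false result in favour of Group I. It is 2.5% with no gap, 3.0% with 1 day and 4.9% with 3 days. The uncorrected test is the one the SAP implies here, since expected counts of about 15 exceed its limits for Yates or Fisher.

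**The case against.** A reader might infer that the plan deletes early Group I cases. The documents do not support that.

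- The sentence closes the section on the entry smear, a step that both groups take before preventive observation. Non-inclusion is the Protocol's term for failing entry, as distinct from exclusion afterwards.
- It matches inclusion criterion 5, "A negative result of a PCR study for the presence of SARS-CoV-2 RNA according to the biomaterial obtained by nasopharyngeal", which applies to both groups. Inclusion and non-inclusion criteria are checked again at Visit 1.
- A positive PCR is not among the ten exclusion criteria, so no listed rule removes a randomised participant for it.
- The case-confirmation text has no restriction by group and applies to Group I as much as to Group II.
- No PCR is scheduled between Visit 1 and the first dose, so an unscheduled test is needed. An entry result could also arrive late, since "Randomization of the study participants is carried out on the same day or the next day after signing the informed consent". But a late positive entry result would breach criterion 5 in Group II as well, so that route need not be one-sided.

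All of this stands, and it makes entry screening the likelier meaning. It does not remove the conflict. The second smear rule goes beyond entry to tests during and after the course. The antibody paragraph concerns symptomatic participants with a negative PCR, so it does not directly govern positives. The exposure condition in SAP section 5.5 is in force whatever the smear section was meant to say.

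A larger figure is also tempting. The Protocol cites 14% incidence in controls, but for medical workers at high exposure; its planning range is 1 to 5%. Infections already incubating at entry might make the first days heavier than a constant hazard implies, while the requirements of no symptoms and a recent negative PCR might make them lighter. The documents settle neither.

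**Conclusion.** The point holds as a conflict over time zero, with a possible one-sided loss of events, and not as a stated rule that erases Group I cases. On the literal wording, the smear rule and the SAP's ITT definition together allow a Group I participant who is PCR-positive before the first dose to be dropped, while a Group II participant positive on the same day is counted.

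The size is small: at most about 0.1 to 0.6 Group I cases for a 1-day gap and about 0.3 to 1.7 for a 3-day gap, at 1 to 5% incidence. Real numbers would be lower, since the smear rule reaches only PCR-positive cases found by an unscheduled test. These figures rest on 315 per group, a constant hazard and an assumed gap. The direction is not in doubt: any loss would favour the drug, in an open-label trial that expects few events.

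**What to change.** Make three changes together.

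1. Protocol, Nasopharyngeal smear: in the first rule, replace the reference to the start of the drug with *before randomisation*. In the second, replace the reference to the preventive course with *at any time after randomisation*.
2. SAP section 5.5: delete the exposure condition from the ITT definition, so that ITT means all randomised participants in their assigned group. Changing the Protocol alone would leave this route open.
3. State in both documents that every case after randomisation counts in the assigned group, in both groups, whether or not a first dose was taken.

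The cost is a few phrases and no new data. Isolation and clinical handling of a positive participant stay as they are. If the sponsor already meant this, the edit only records it; otherwise the Group I rate may be slightly less favourable.
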